#### SECTION VIII: RESEARCH ALTERNATIVES AND ECONOMIC CONSIDERATIONS

1. **Alternatives:** What other alternatives, if any, are available to the study participants outside of the research?

All participants and potential participants will be provided with a list of community referrals, including medical, HIV/STD testing, psychological, substance use, and housing supports.

2. **Payments for Participation (Economic Considerations):** Describe any payments that will be made to participants, if any, the amount and timing of payments and the conditions for receiving this compensation (if applicable). If you plan to hold a drawing, be sure to include the following on any consent or recruitment materials mentioning the sweepstakes: 1) the value of the prize; 2) the sponsor of the prize (this cannot be a federal funding source); 3) the odds of winning; 4) that there are no restrictions to winning.

Participants will receive \$25 for completing each of the two baseline assessments (baseline 1 and baseline 2), \$50 for completing the 4-month and 8-month follow-up assessments, and \$75 for

completing the final 12-month follow-up assessment (total = \$225). Participants randomized to the ESTEEM condition and CMHT condition will receive \$10 per session for \$10 sessions (total = \$100). Therefore, depending on condition assignment, participants will receive between \$225 and \$325 for completing all aspects of the study. Payment will be prorated for partial study completion (i.e., participants will only be paid for the parts of the study that they completed).

Throughout the course of the study, we will hold a monthly sweepstakes at the New York site for participants who have completed their 4-month, 8-month, or 12-month follow-up appointments in the previous month. This sweepstakes winner will be selected using a random number generator. Winners will receive a \$20 gift card which will be emailed to them directly after the selection of the sweepstakes winner. Participants will be notified about the sweepstakes prize, odds of winning, and prize sponsor in their monthly appointment reminder emails from the ESTEEM research team.

Annually, we will also hold a sweepstakes at the New York site for all randomized New York participants who successfully completed all of their follow up assessments (4, 8, and 12 month). This sweepstakes will occur every October beginning in 2018 and ending in 2021. Winners will be selected using a computer random number generators and receive a \$200 gift card via email. The annual sweepstakes will be explained to participants during their first appointment and clearly explained during the consent process in the ICF.

The sweepstakes will only take place in New York due to the differential cost of living in New York city compared to that of Miami. According to the US Census cost of housing in Miami is 7.7% greater than the national average, where comparatively the cost of living in New York city is 286.7% the national average. However, to maintain as much parity between sites we will account for the differential cost of living through the possibility to earn additional compensation through the sweepstakes.

Participants will also receive welcome bags with upon randomization into the study. The value of the welcome bags will be approximately \$5.00-\$10.00 and will include condoms, lubricant packets, a lanyard, candy, a welcome card, stickers, a pen, and a stress ball.

- 3. Costs for Participation (Economic Considerations):** Clearly describe the participant's costs associated with participation in the research, if any, and the interventions or procedures of the study that will be provided at no cost to participants. If participants screen inconclusive or receive an HIV+ result during the rapid HIV testing, the testing site provides the confirmatory testing at no cost to the study and bills the participant directly if either the testing site or participant insurance is unable to cover the costs. Either way, it will be at no cost to the participant. Participants are welcome to use their private insurance for any confirmatory testing.

Study participation will generate no cost for participants. All study treatment (ESTEEM, CMHT, VCT) will be provided free of charge to all study participants.

---

 C2ER, Arlington, VA, ACCRA Cost of Living Index, Annual Average 2010 (copyright).

SECTION IX:  
PRINCIPAL INVESTIGATOR AGREEMENT

As the **principal investigator** of this research project, I certify that:

1. The information provided in this application is complete and accurate.

APPENDIX A. Prototype DSMB Tables, Listing, and Figures

STATISTICAL ANALYSIS PLAN

STUDY SUMMARY (revised 9/14/2020)

Title	A unified intervention for young gay and bisexual men's minority stress, mental health, and HIV risk (ESTEEM)
Study Design	The design is a three-arm, parallel-assignment randomized controlled trial design to test the efficacy of ESTEEM (Effective Skills to Empower Effective Men) with two comparison conditions—LGBTQ (lesbian, gay, bisexual, transgender, queer)-affirmative community mental health treatment (CMHT) and brief voluntary HIV counseling and testing (VCT) only. The unit of randomization is the individual.
Study Duration	5 years
Trial Sites	2 trial sites: New York City (Yale School of Public Health, Yale University) and Miami, Florida (University of Miami)
Objective	Conduct a randomized controlled trial to test the efficacy of a 10-session skills-building intervention designed to reduce young gay and bisexual men's co-occurring health risks by addressing the underlying cognitive, affective, and behavioral pathways through which minority stress impairs health.
Number of Subjects	The original target sample size was 250 participants enrolled from the two study sites [New York: 150 (60 ESTEEM, 60 CMHT, 30 VCT) and Miami: 100 (40 ESTEEM, 40 CMHT, 20 VCT)]. In our pilot study, we saw a 60% reduction in primary outcome at 6 months in the ESTEEM arm. We used these estimates to inform our 8-month endpoint. To achieve at least 90% power at a 5% type I error rate, accounting for an R-square of 0.1 between treatment arm and site, we expected needing 80 individuals in the ESTEEM and CMHT arms, and 40 individuals in the VCT-only arm. Although we planned to take steps to increase our retention rate from our pilot study, we conservatively estimated the retention at 8 months to be 80%, thus increasing the total sample size to a target sample size of 250. The target sample size was revised on 2/28/18 to correct an imbalance in randomization; recruitment ended after 44 months on DATE with a total of 254 participants enrolled.
Main Inclusion Criteria	(1) aged 18–35, (2) identify as a gay or bisexual man, (3) HIV-negative status confirmed through in-office testing, (4) diagnosis of any Diagnostic and Statistical Manual (DSM-5) depressive, anxiety, or trauma- and stressor-related disorder; (5) HIV sexual risk (≥ 1 act in past-90-day of condomless anal sex with a male partner of unknown status or HIV+ status, unless with a HIV+ primary/main partner with known undetectable viral load); (6) not currently adherent to PrEP (pre-exposure prophylaxis) (defined as taking 4 or more days per week) (7) NYC or Miami residential stability and planned availability for 12 months; and (8) provision of informed consent.

STATISTICAL ANALYSIS PLAN

Intervention	ESTEEM is a 10-session intervention based on the Unified Protocol, an individually-delivered cognitive behavioral therapy (CBT) intervention with efficacy for reducing stress-sensitive mental health disorders (e.g., depression, anxiety) by enhancing emotion regulation skills; reducing avoidance patterns; and improving motivation and self-efficacy for behavior change. The Unified Protocol employs modules for motivation enhancement, interoceptive and situational exposure, cognitive restructuring, mindfulness, and self-monitoring techniques. Through an extensive adaptation process, we adapted the Unified Protocol to enhance young gay and bisexual men’s stigma coping by reducing minority stress processes.
Duration of Intervention	10 therapy sessions in 4 months.
Primary Outcome	The primary outcome is condomless anal sex in the absence of either PrEP or known undetectable viral load of HIV+ primary partners, measured with the Time-Line Follow-Back (TLFB), a semi-structured interview. The TLFB yields past-90-day incidence of HIV risk behavior: condomless anal sex, sex while using drugs or alcohol, number of sexual partners, and preceding-week PrEP use (i.e., coverage defined as 4+ doses per week). TLFB interviewers are masked to study arm. The primary outcome is assessed at 8-month follow-up.
Primary Analysis	We will use a fixed sequence procedure (gatekeeper strategy) to control for multiple testing of the primary comparisons: reduction in condomless anal sex in ESTEEM vs. VCT-only and ESTEEM vs. CMHT. We will conduct the comparison of ESTEEM versus VCT-only at the 0.05 level. If we find statistical significance between ESTEEM vs. VCT-only, then we will test the second comparison ESTEEM vs. CMHT at 0.05. To make use of all data collected, we will analyze the condomless anal sex outcome using a generalized linear mixed model with a logit link using a contrast to test the comparison at the primary time point of 8 months adjusting for site.
Secondary Outcomes	Depression severity, anxiety, drug abuse, alcohol abuse, mental health diagnoses, suicidality, minority stress and universal stress processes

STATISTICAL ANALYSIS PLAN

1. BACKGROUND

Young gay and bisexual men (YGBM) are at disproportionate risk of depression, anxiety, and substance use problems, which synergistically fuels their increasing risk of HIV infection. Among young men, approximately 93% of all diagnosed HIV infections are male-to-male. Mental health and substance use disparities drive YGBM's HIV- risk behavior. Despite HIV risk being influenced by mental health disparities for YGBM, no evidence based mental health intervention specifically tailored to this population exists. YGBM health interventions currently use a one-problem/one-treatment approach. Some interventions promote condom use, some encourage PrEP initiation and maintenance, and others reduce substance use. These treatments show moderate efficacy. None currently seeks to reduce mental health problems (e.g., depression, anxiety) among at-risk YGBM. A unified, transdiagnostic approach that addresses the pathways that unite these conditions may increase effectiveness, reduce cost, and provide a streamlined treatment experience for the most vulnerable YGBM, who are unlikely to seek multiple treatments for multiple health concerns.

ESTEEM (Effective Skills to Empower Effective Men) is a 10-session skills-building intervention designed to reduce YGBM co-occurring health risks by reducing the underlying cognitive, affective, and behavioral pathways through which minority stress impairs YGBM's health. ESTEEM is based on the Unified Protocol, a cognitive-behavioral therapy (CBT) approach with efficacy across mental health and risk behaviors. The Unified Protocol changes underlying stress pathways using motivational interviewing, emotional and situational exposure, cognitive restructuring, mindfulness, and self-monitoring exercises. To create ESTEEM, through an NIMH R34 award, our team adapted the Unified Protocol by conducting interviews with 21 YGBM-expert mental health providers and 20 depressed, anxious YGBM at high risk for HIV infection. These stakeholders helped our team infuse the Unified Protocol with minority stress coping content.³⁴ ESTEEM aims to normalize the adverse impact of minority stress, reduce internalized homophobia and rejection schemas, reduce YGBM's unhealthy avoidance tendencies (e.g., substance use during sex, condom use non-assertion), and validate YGBM's unique strengths. In a preliminary trial (n=63), ESTEEM significantly reduced YGBM's spectrum of interrelated health threats, making it the first evidence-based intervention to simultaneously improve mental health, substance use, and sexual health outcomes among YGBM. However, important questions remain in order to validate the efficacy and potential cost-effectiveness of ESTEEM.

2. AIMS

1. **Aim 1:** Test the efficacy of ESTEEM against (1) community mental health treatment (CMHT) and (2) HIV/STD voluntary counseling and testing (VCT).
2. **Aim 2:** Determine whether ESTEEM works through its hypothesized cognitive, affective, and behavioral minority stress processes. 4-, 8-, and 12-month follow-ups will determine if improvements in minority stress processes precede and statistically mediate outcome improvements.

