**Condition 1: ESTEEM.** ESTEEM is a 10-session intervention based on the Unified Protocol, an individually-delivered CBT intervention with efficacy for reducing stress-sensitive mental health disorders (e.g., depression, anxiety) by enhancing emotion regulation skills; reducing avoidance patterns; and improving motivation and self-efficacy for behavior change. The Unified Protocol employs modules for motivation enhancement, interoceptive and situational exposure, cognitive restructuring, mindfulness, and self-monitoring techniques. Through an extensive R34 adaptation process described above, we adapted the Unified Protocol to enhance YGBM's stigma coping by reducing minority stress processes. For example, modules were adapted to help YGBM identify minority stress experiences; track unhealthy reactions to minority stress, focusing on avoidance reactions, like substance use and condomless anal sex; attribute distress to minority stress rather than to personal failure; and assert themselves against unjust minority stress in safe situations. Adaptations were infused throughout the Unified Protocol *Therapist Workbook*; this adaptation served as the therapist manual. The full manual is attached. ESTEEM participants will complete 10 sessions of therapy, with one session per week. If participants miss sessions or need to reschedule, we will make every effort to reschedule sessions such that participants stay as close to a one session per week schedule. If participants miss a week, they may be rescheduled to do two sessions in one week, but they will be told the goal is once per week. All sessions must be completed within four months.

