|  Through local NGO or other local contact       |  Social Media (Facebook, Twitter) |   |
|  Classroom recruitment                                     |  |   |
|  Table set-up / in-person recruitment of public |  |   |
|  Snowball sampling                              |  |   |
|  Other (describe):   |  |   |

3. **Targeted Enrollment: Give the number of participants:**

1. Targeted for enrollment at Yale (site: New York) for this protocol: 150
2. If this is a multi-site study, give the total number of participants targeted across all sites:

New York: 150 (60 ESTEEM, 60 CMHT, 30 VCT)

Miami: 100 (40 ESTEEM, 40 CMHT, 20 VCT)

4. **How was this estimate derived?**

Our primary goal is to demonstrate a greater reduction at 4, 8, and 12 months in “unprotected sex” as defined as past-90-day condomless anal sex without PrEP or with HIV+ or status-unknown casual partners or with HIV+ primary partners without known undetectable viral load, in the ESTEEM arm versus the CMHT and VCT arms. In our pilot study, we saw a 60% reduction in condomless anal sex at 6 months in the ESTEEM arm. Based on previous studies of VCT and the fact that CMHT does not specifically focus on condomless anal sex, we expect that these arms will yield lower reductions compared to ESTEEM, but a slightly larger reduction in CMHT (20%) compared to VCT (15%). To achieve at least 90% power at a 5% type I error rate, accounting for an R-square of 0.1 between treatment arm and the covariates, we will need 80 individuals in the ESTEEM and CMHT arms, and 40 individuals in the VCT arm. Although we plan to take steps to increase our retention rate from our pilot study, we conservatively estimate the retention at 6 months to be 80%. Therefore, we plan to randomize 100 ESTEEM, 100 CMHT and 50 VCT YGBM. Sample size calculations were carried out using PASS 12 (Kaysville, Utah) for logistic regression. For secondary outcomes (e.g., mental health, substance use), we will have 80% power to detect an effect size of 0.55 and 0.70 for ESTEEM vs. CMHT and ESTEEM vs. VCT, respectively, at a type I error rate of 0.01 (conservative due to multiple testing). These effect sizes are smaller than those found in the pilot.

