4.1 Primary Outcome

The primary outcome is condomless anal sex at 8-month time point (binary: Yes/No) in the absence of either PrEP or known undetectable viral load of HIV+ primary partners, measured with the Time-Line Follow-Back (TLFB), a semi-structured interview. The TLFB will yield past-90-day incidence of HIV risk behavior: condomless anal sex, sex while using drugs or alcohol, number of sexual partners, and preceding-week PrEP use (i.e., coverage defined as 4+ doses per week). The primary outcome is measured every 4 months (4, 8, 12 months).

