4.2 Secondary Outcomes

Condomless anal sex at 12 months (binary); Condomless anal sex at 8 and 12 months (count); Depression severity, as measured using the HAMD depression severity score, ODSIS, and BSI at 8 and 12 month time points; Anxiety, as measured by the BAI, OASIS, BSI, and SIAS at 8 and 12 month time points; Drug abuse, as measured by the SIP-D at 8 and 12 month time points; Alcohol abuse, as measured using by the AUDIT at 8 and 12 month time points; Mental health, as defined by odds of no longer having at least one *DSM-5* diagnosis (e.g., depression, anxiety) that was present at baseline still be present at 8 and 12 month time points based on the MINI (binary); Suicidality as measured by SIDAS at 8 and 12 month time points (continuous); Minority stress as captured by rejection sensitivity measured using RS, internalized homophobia measured using IHS and IAT; and sexual orientation concealment measured using SOCS at 4 and 8 month time points (continuous); Universal stress processes as captured by emotional regulation as measured by DERS, rumination as defined by RRS, assertiveness as measured by RAS, social support as measured by MSPSS, cognitive bias as measured by SRET, and impulsivity measured by Go/No-Go at 4 and 8 month time points (continuous).

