6.2 Sample Size Determination for the Primary Outcome

Sample size calculations were carried out using PASS 12 for logistic regression.

Our primary goal is to demonstrate a greater reduction at 8 months in condomless anal sex in the absence of either PrEP or known undetectable viral load of HIV+ primary partners, in the ESTEEM arm versus the CMHT and VCT-only arms. In our pilot study, we saw a 60% reduction in condomless anal sex at 6 months in the ESTEEM arm. We used these estimates to inform our 8-month endpoint.

Based on previous studies of VCT and the fact that CMHT does not specifically focus on condomless anal sex, we expect that these arms will yield lower reductions compared to ESTEEM, but a slightly larger reduction in CMHT (20%) compared to VCT-only (15%). To achieve at least 90% power at a 5% type I error rate, accounting for an R-square of 0.1 between treatment arm and the covariates (e.g., site, race/ethnicity), we will need 80 individuals in the ESTEEM and CMHT arms, and 40 individuals in the VCT-only arm. Although we plan to take steps to increase our retention rate from our pilot study, we conservatively estimate the retention at 8 months to be 80%. Therefore, we planned to randomize 100 ESTEEM, 100 CMHT, and 50 VCT-only young gay and bisexual men. The original target sample size was 250 participants enrolled from the two study sites [New York: 150 (60 ESTEEM, 60 CMHT, 30 VCT) and Miami: 100 (40 ESTEEM, 40 CMHT, 20 VCT)]. This was increased to 254 on 2/28/18 to correct an imbalance in the 2:2:1 randomization. The final sample size was 254.

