8.4.3 Minority Stress- Mediation analysis

We plan to model minority stress mediators (rejection sensitivity, internalized homophobia, sexual orientation concealment) as a latent variable at the 4- and 8-month time points. We will then use these constructs in latent variable mediation models using structural equation modeling to examine whether 4-month minority stress mediates 8-month sexual risk and mental health outcomes; and whether 8-month minority stress mediates 12-month sexual risk and mental health outcomes. The mediation models will include test of exposure-mediation interactions (Valeri and VanderWeele 2013; Muthan and Asparoutov 2015), to consider potential confounding of the mediation-outcome relationship and allow for causal interpretation. In case of support for a mediating effect of minority stress in the above latent variable mediation model, we will apply a sequential approach in our analyses of mediation to estimate both the joint effect through all mediations, as well as, give consideration to how much of the combined effect is attributed to each mediator (Vansteelandt and Daniel 2017; VanderWeele and Vansteelandt 2014).

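### No 4-month between-arm contrast is planned for sexual-risk, mental health, substance use or diagnosis outcomes, and the lagged mediation models cannot show that stress-process change came before outcome change

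*SAP*

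**What the plan says.** **Aim 2.** SAP section 2 states that "4-, 8-, and 12-month follow-ups will determine if improvements in minority stress processes precede and statistically mediate outcome improvements".

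**Time points of the goal.** The sample-size rationale in Protocol Section V, item 4, says "Our primary goal is to demonstrate a greater reduction at 4, 8, and 12 months". SAP 6.2 restates it as "Our primary goal is to demonstrate a greater reduction at 8 months in condomless anal sex". The SAP gives no reason for leaving out month 4.

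**Treatment window.** For both therapy arms, Protocol Section IV says "All sessions must be completed within four months". Month 4 is therefore the end-of-treatment visit.

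**Data collected.** SAP 4.1 schedules the primary outcome at months 4, 8 and 12. SAP Table 1 schedules the depression, anxiety, substance use, suicidality and diagnosis measures every four months.

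**Contrasts specified.**
- Binary condomless sex: month 8 (SAP 8.3.1) and month 12 (8.4.1).
- Count of acts: months 8 and 12 (4.2, 8.3.2, 8.4.1).
- Continuous mental health and substance use scales: months 8 and 12 (8.4.2.1).
- MINI diagnosis: months 8 and 12 (8.4.2.2).
- Minority and universal stress processes: secondary outcomes at months 4 and 8 (4.2).

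**Mediation.** SAP 8.4.3 will "examine whether 4-month minority stress mediates 8-month sexual risk and mental health outcomes", then take the 8-month mediator to the 12-month outcome. SAP 8.4.4 does the same for the universal stress processes. The only step named against mediator-outcome confounding is a test of exposure-mediator interaction.

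**The concern.** There are two consequences.

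1. Month 4 is where a treatment effect could be largest. Without a contrast there, a null result at month 8 could mean that ESTEEM never worked, or that it worked during therapy and the effect faded. Nothing planned separates the two.

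2. Aim 2 claims an order of change. Mediator and outcome are first remeasured together at month 4. Suppose therapy improved the outcome by then and the stress measures improved as a result. Because the outcome carries over from month 4 to month 8, the 4-month mediator would still predict the 8-month outcome and the lagged model could report mediation. An interaction test does not address this. Nor does adjustment for baseline mediator and baseline outcome, because the problem arises between baseline and month 4.

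**Working it through.** **1. Reading the time points side by side**

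| Measure | Collected at month 4? | Arm contrast specified |
|---|---|---|
| Condomless sex, binary | yes | 8, 12 |
| Condomless sex, count | yes | 8, 12 |
| Depression, anxiety, drug, alcohol, suicidality scales | yes | 8, 12 |
| MINI diagnosis | yes | 8, 12 |
| Stress processes | yes | listed at 4 and 8, but analysed in 8.4.3 and 8.4.4 only as mediators |

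The SAP study summary says the primary mixed model is meant to use all collected data, so 4-month values may enter it. The only primary contrast named is month 8.

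**2. Timing of the behaviour measure**

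The TLFB looks back 90 days, about 3 months. The 8-month report covers about months 5 to 8 (8 − 3 = 5), after the 4-month mediator. The 4-month report covers about months 1 to 4 and overlaps therapy.

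**3. Can the lagged model tell outcome-first from mediator-first?**

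The only design input is 80 per arm (SAP 6.2, ESTEEM and CMHT after dropout). Every path value below is an assumption; the documents give none. Variables are in SD units, with T = 1 for ESTEEM.

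Outcome-first model, with no effect of the mediator on the later outcome:
- Y0 = 0.3·M0 + error
- Y4 = 0.5·Y0 − e·T + error (variance 0.75)
- M4 = 0.5·M0 + s·Y4 + error (variance 0.75)
- Y8 = c·Y4 + error (variance 1 − c²)

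Fitted: path a, M4 on T, M0 and Y0; path b, Y8 on T, M4, M0 and Y0. Mediation is declared when both paths have |t| > 1.96. The adjusted fit adds Y4 to path b.

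| e | s | c | Lagged model | With Y4 added |
|---|---|---|---|---|
| 0 | 0.5 | 0.5 | 4% | 0.2% |
| 0.3 | 0.3 | 0.5 | 3% | 0.5% |
| 0.55 | 0.3 | 0.5 | 8% | 1% |
| 0.55 | 0.5 | 0.5 | 32% | 2% |
| 0.55 | 0.5 | 0.7 | 41% | 2% |
| 0.7 | 0.3 | 0.7 | 20% | 1–2% |
| 0.7 | 0.5 | 0.7 | about 60–65% | about 3% |

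The rate rises with the early effect e, the slope s and the carry-over c. With weak paths it stays near or below 5%.

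**4. The opposite case**

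Mediator-first model: therapy moves the mediator by 0.5 to 0.7 SD, the mediator moves the 4-month outcome with slope 0.3 to 0.5, and carry-over is 0.6. Mediation is now real.

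| Further direct path M4 to Y8 | Lagged model detects | With Y4 added |
|---|---|---|
| none | about 50–92% | about 5% |
| 0.1 | about 84–99% | about 21–26% |

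Here the 4-month outcome lies on the causal path, so adjusting for it removes most of the real effect. Neither model identifies the order of change between baseline and month 4.

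**The case against.** Several parts of the case for the plan stand.

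- *Eight months is a legitimate single primary time point.* The protocol sentence naming three visits is a sample-size rationale, and the SAP aligns goal, power and retention at month 8. This is a reason to keep the primary test as it is. It is not a reason to leave an end-of-treatment effect without any estimate.
- *A reader might infer that the SAP has no 4-month endpoint at all.* It does: the stress processes are secondary outcomes at months 4 and 8. The gap concerns sexual risk, mental health, substance use and diagnosis.
- *A reader might infer that precedence is never examined.* Both mediation models measure the mediator one visit earlier, and the 8-month TLFB window falls after the 4-month visit. What is missing is evidence on the order of change.
- *A reader might infer that fading effects go unreported.* Fading from month 8 to 12 is covered by the 12-month endpoints. Only fading from month 4 to 8 has no planned estimate.
- *Some by-visit output exists.* SAP 8.4.2.1 gives means by treatment and time point if treatment-by-time interaction is present, but this is conditional, applies to the continuous scales, and sits under an 8- and 12-month endpoint. The DSMB summaries by time point (SAP 7.2) are not efficacy estimates.
- *The simulations are not this trial.* They use a continuous outcome and ordinary regression. The SAP plans latent-variable structural equation models, and the primary outcome is binary. They show a mechanism and its direction, not an expected error rate.

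It is also tempting to conclude precedence only if the mediator path survives adjustment for the same-visit outcome. The mediator-first case shows why that rule fails: it would reject genuine mediation completed by month 4.

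**Conclusion.** The point holds in two limited parts.

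First, the SAP specifies no 4-month arm contrast for condomless sex, mental health, substance use or diagnosis, although the data are collected and the protocol's primary goal names that visit. This follows from the text alone.

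Second, the lagged models in 8.4.3 and 8.4.4 cannot show that stress-process change preceded outcome change, because they list no outcome at the mediator's visit. Under assumed outcome-first paths (early effect 0.3 to 0.7 SD, slope 0.3 to 0.5, carry-over 0.5 to 0.7, 80 per arm, baseline adjusted) they declare mediation in roughly 5% to 65% of trials when there is none. The size depends on paths the documents do not supply; the direction does not.

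The remaining limit comes from the visit schedule and cannot be modelled away. The confirmatory 8-month comparison and its type I error control are untouched.

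**What to change.** 1. **4-month contrasts.** In SAP 4.2 and 8.3 to 8.4.2, add month-4 arm contrasts for condomless sex (binary and count), the mental health and substance use scales, and MINI diagnosis, taken from the repeated-measures models already planned. Label them secondary, keep them outside the 8-month gatekeeper, and place the scale contrasts within the existing false-discovery-rate control. Note that the 4-month TLFB window overlaps therapy.
2. **Mediation sensitivity analyses.** In 8.4.3 and 8.4.4, keep the planned lagged model. Beside it, fit a version that includes the outcome at the mediator's visit (month 4 for the 4-to-8 model, month 8 for the 8-to-12 model), and the reverse lag from 4-month outcome to 8-month mediator. Do not make survival of the adjusted path a condition for claiming precedence.
3. **Aim 2 wording.** State that the order of change within the first four months is not identified, because mediator and outcome are first remeasured together.

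Cost: SAP text, contrasts and model terms on data already collected, with no new visits or participants. The downsides are more secondary estimates, which enlarge the false-discovery-rate family, and an adjusted indirect effect that is conservative when mediation acts before month 4.
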